#### 3.2 Exclusion Criteria

- 1. Patients who have had chemotherapy or radiotherapy within 4 weeks (6 weeks for nitrosoureas or mitomycin C) prior to entering the study or those who have not recovered from adverse events due to agents administered more than 4 weeks earlier.
- 2. Patients who are receiving any other investigational agents.
- 3. History of allergic reactions attributed to compounds of similar chemical or biologic composition to nivolumab.
- 4. Prior allogeneic transplantation, since such individuals have increased risk of complications from nivolumab.
- 5. Uncontrolled intercurrent illness including, but not limited to, ongoing or active infection, symptomatic congestive heart failure, unstable angina pectoris, cardiac arrhythmia, or

psychiatric illness/social situations that would limit compliance with study requirements.

- 6. Any condition requiring >10 mg/d prednisone equivalents
- 7. Current or prior HTLV-1 associated inflammatory diseases, including but not limited to myelopathy, uveitis, arthropathy, pneumonitis, or a Sjögren's disease-like disorder.
- 8. Prior treatment with anti-PD-1, anti-PD-L1, anti-PD-L2 antibody.
- 9. Grade 2 or greater toxicity from prior therapy.
- 10. Grade 2 or greater diarrhea.
- 11. Autoimmune disease: Patients with active autoimmune disease or history of autoimmune disease that might recur, which may affect vital organ function or require immune suppressive treatment including systemic corticosteroids, should be excluded. These include but are not limited to patients with a history of immune related neurologic disease, multiple sclerosis, autoimmune (demyelinating) neuropathy, Guillain-Barré syndrome, myasthenia gravis; systemic autoimmune disease such as SLE, connective tissue diseases, scleroderma, inflammatory bowel disease (IBD), Crohn's, ulcerative colitis, hepatitis; and patients with a history of toxic epidermal necrolysis (TEN), Stevens-Johnson syndrome, or phospholipid syndrome should be excluded because of the risk of recurrence or exacerbation of disease. Patients with vitiligo, endocrine deficiencies including thyroiditis managed with replacement hormones including physiologic corticosteroids are eligible. Patients with rheumatoid arthritis and other arthropathies (other than HTLV-associated arthropathy), and psoriasis controlled with topical medication and patients with positive serology, such as antinuclear antibodies (ANA), anti-thyroid antibodies should be evaluated for the presence of target organ involvement and potential need for systemic treatment but should otherwise be eligible.

Patients are permitted to enroll if they have vitiligo, type I diabetes mellitus, residual hypothyroidism due to autoimmune condition only requiring hormone replacement, psoriasis not requiring systemic treatment, or conditions not expected to recur in the absence of an external trigger (precipitating event).

- 12. Patients who have had evidence of active or acute diverticulitis, intra-abdominal abscess, GI obstruction and abdominal carcinomatosis which are known risk factors for bowel perforation should be evaluated for the potential need for additional treatment before coming on study.
- 13. Patients who have Hepatitis C (both reactive anti-HCV antibody and detectable HCV RNA) and Hepatitis B (HBsAg positive and anti-HBc-Total positive), may be enrolled, provided their total bilirubin: ≤1.5× institutional upper limit of normal (ULN) AST (SGOT) /ALT (SGPT): ≤2.5 X institutional upper limit of normal.

- 14. Patients with concurrent HIV infection may be enrolled if compliant with 3 or more drug anti-retroviral regimen and virus load less than 50 copies/ml and CD4 count greater than 250 cells/ml, and no concurrent opportunistic infection or other malignancy.
- 15. Any other prior malignancy from which the patient has been disease free for less than 3 years, with the exception of adequately treated and cured basal or squamous cell skin cancer, superficial bladder cancer, carcinoma in situ of any site or any other cancer.
- 16. Pregnant women are excluded from this study because nivolumab is an agent with the potential for teratogenic or abortifacient effects. Because there is an unknown but potential risk for adverse events in nursing infants secondary to treatment of the mother with nivolumab, breastfeeding should be discontinued if the mother is treated with nivolumab.

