# **5.2.3 Prohibited Therapies**

Patients in this study may not use vaccines for the treatment of cancer for up to one month pre and post dosing with nivolumab. Concomitant systemic or local anti-cancer medications including biologics, or radiation therapy treatments are prohibited in this study while receiving nivolumab.

Patients may not use any of the following therapies during the study:

- Any non-study anti-cancer agent (investigational or non-investigational)
- Any other investigational agents
- CTLA4 antagonists, CD137 agonists, PD-1 inhibitors
- Immunosuppressive agents, unless indicated to manage study therapy induced immunerelated adverse events (irAEs)
- Chronic systemic corticosteroids, unless indicated to manage study therapy induced irAEs or chronic graft-versus-host disease (GVHD) at a stable dose prior to study entry

• Any non-oncology vaccine therapies used for the prevention of infectious diseases (for up to 30 days prior to or after any dose of study drug, however it is suggested that routine vaccinations, including seasonal influenza, be given at least 2 weeks prior to study treatment).

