#### **13.4.2** Evaluation of Response

All patients included in the study must be assessed for response to treatment, even if there are major protocol treatment deviations or if they are ineligible. Each patient will be assigned one of the following categories: 1) complete response, 2) partial response, 3) stable disease, 4) progressive disease, 5) early death from malignant disease, 6) early death from toxicity, 7) early death because of other cause, or 8) unknown (not assessable, insufficient data). [Note: By arbitrary convention, category 8 usually designates the "unknown" status of any type of data in a clinical database.]

All of the patients who met the eligibility criteria (with the possible exception of those who received no study medication) should be included in the main analysis of the response rate. Patients in response categories 4-9 should be considered to have a treatment failure (disease progression). Thus, an incorrect treatment schedule or drug administration does not result in exclusion from the analysis of the response rate. Precise definitions for categories 4-9 will be protocol specific.

All conclusions should be based on all eligible patients. Subgroup analyses may then be performed on the basis of a subset of patients, excluding those for whom major protocol deviations have been identified (*e.g.*, early death due to other reasons, early discontinuation of treatment, major protocol violations, etc.). However, these subgroup analyses may not serve as the basis for drawing conclusions concerning treatment efficacy, and the reasons for excluding patients from the analysis should be clearly reported. The 95% confidence intervals should also be provided.

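### The closing words of exclusion item 15 make its exception as broad as its rule, so the 3-year disease-free limit has no clear effect

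*Combined protocol and SAP*

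**What the plan says.** Section 3.2, item 15, states its rule first: "Any other prior malignancy from which the patient has been disease free for less than 3 years". The exceptions follow in the same sentence. They open "with the exception of adequately treated and cured basal or squamous cell skin cancer", go on to superficial bladder cancer, and close "carcinoma in situ of any site or any other cancer".

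Other provisions touch the same patients without restating the 3-year limit:

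- Section 3.2, item 1, excludes "Patients who have had chemotherapy or radiotherapy within 4 weeks (6 weeks for nitrosoureas or mitomycin C) prior to entering the study".
- Section 3.2, item 9, excludes patients with toxicity of grade 2 or higher left from earlier treatment.
- Section 3.2, item 14, admits patients with HIV only if there is "no concurrent opportunistic infection or other malignancy".
- Section 5.2.3 bans, during the study, "Any non-study anti-cancer agent (investigational or non-investigational").
- Section 4.3 has the lead investigator or a designee review each eligibility checklist and its source documents before registration.

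For the analysis, section 13.4.2 says: "All conclusions should be based on all eligible patients". Section 13.2 defines evaluable patients as those who received study medication.

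**The concern.** The rule applies to every other malignancy, and the last exception appears to do the same. An exception as wide as its rule leaves nothing for the rule to do. A screener who faces a patient with a solid tumour treated a few months earlier finds one half of the sentence excluding that patient and the other half apparently admitting the same patient.

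The main thing at stake is the reading of response. Section 11.1.4 counts a new lesion as relapse or progression, so a recurrence of the second cancer could be scored as progression of ATLL. Section 2.2 reports nivolumab activity in melanoma, non-small cell lung cancer and renal cell carcinoma, so shrinkage of such a lesion could also be read as an ATLL response. Section 13.4.2 counts early death from another cause as treatment failure. Because that section rests conclusions on eligible patients, an unclear criterion also leaves room to dispute, once results are known, whether a given patient belongs in the response analysis.

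**Working it through.** No formula applies to the wording itself. The check is to set out the possible readings and apply each to one illustrative patient: a second cancer that is none of the named types, treated 6 months before entry, with no evidence of disease since.

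| Reading of item 15 | Judged cured | Not judged cured |
|---|---|---|
| (a) The treated-and-cured qualifier governs skin cancer only; the closing words are a separate exception | Not excluded | Not excluded |
| (b) The qualifier governs the whole list | Not excluded | Excluded |
| (c) The closing words extend carcinoma in situ: in situ of any site, or of any other cancer | Excluded | Excluded |
| Last four words deleted | Excluded | Excluded |

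1. Under (a), every cancer is excepted without condition and item 15 excludes no one.
2. Under (b), the 3-year interval is void for any cancer called cured. The protocol does not say who decides this, or by what standard.
3. Under (c), the limit survives. The reader must supply a word, however, and the phrase then repeats what the reference to any site already covers. This reading is possible but strained.
4. Under (a) and (b), naming individual cancer types serves no purpose, because the last exception takes them all in. That points to a drafting error and not to an intended widening.
5. Neither the inclusion criteria nor the registration sections contain a second statement of the 3-year limit that could settle the reading.

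The weight of one patient follows from section 13.2:

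- Stage 1 has 9 patients: 1/9 = 11.1 percentage points. One response or fewer stops the trial; two or more continue it.
- The final analysis at 20 patients: 1/20 = 5 points. Five responders among 20 to 23 patients are enough for a positive conclusion.
- The final analysis at 25 patients: 1/25 = 4 points. Six responders are needed among 24 or 25.

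One misread response therefore changes a decision only when the count sits at the boundary: 1 against 2 in stage 1, 4 against 5 at 20 to 23 patients, or 5 against 6 at 24 or 25.

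The documents give no rate of recent second cancers in this population. As an assumption, none, one or two affected patients of 20 would amount to 0, 5 or 10 percentage points if every one of them were misclassified. The plan has no figure of its own to reproduce on this point.

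**The case against.** A reader might infer that item 15 admits anyone with a recently treated second cancer and that sites can screen no one out. The documents do not support that. It follows only from reading (a). Under (b), a cancer not judged cured stays excluded. Under any reading, the washout in item 1, the toxicity limit in item 9, the HIV condition in item 14 and the ban in section 5.2.3 each still keep out some of these patients.

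Other protections count too. Section 4.3 gives central confirmation of eligibility before registration, which reduces differences between sites and means that an enrolled patient has normally been ruled eligible. Sections 11.1.7 and 13.2 provide independent review of response. Section 13.4.2 also requires response assessment of ineligible patients, and section 13.2 defines evaluability by receipt of drug. It would therefore be too strong to say that item 15 decides who enters the primary response rate.

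Two further consequences might be inferred and do not hold. The tolerability rule in section 13.3 counts discontinuation for intolerable toxicity, so illness or death from a second cancer does not enter it automatically. Progression-free survival is defined in section 11.1.6 but is neither a primary nor a secondary endpoint in section 13.1.

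All of this stands, and it narrows the consequences. It does not repair the sentence. Central review must apply the same unclear words, and the other criteria address recent treatment, residual toxicity, HIV co-infection and concurrent therapy. None of them addresses the disease-free interval.

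**Conclusion.** Item 15 is wrong as written, with minor severity. On both natural readings its closing words cancel the 3-year limit, wholly under (a) and for any cancer called cured under (b). Only a strained reading preserves it. This is an operative eligibility rule, so the defect is more than a typographical slip in background text.

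The practical effect is probably small. It rests on two assumptions that the documents cannot test: that few enrolled patients will have a recent second cancer, and that such a cancer would have to relapse or regress on study and be misattributed despite independent review. Each patient so misclassified is worth 5 percentage points at 20 patients. No sample size, error rate, power or boundary in section 13 depends on the criterion.

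**What to change.** Delete the last four words of "carcinoma in situ of any site or any other cancer", so that the 3-year limit applies to every malignancy except basal or squamous cell skin cancer, superficial bladder cancer and carcinoma in situ. If the closing words are the start of a clause that was cut off, restore its remainder, provided that the 3-year limit still has effect.

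Deletion alone leaves open whether the treated-and-cured qualifier also governs superficial bladder cancer and carcinoma in situ. The amended item should say so. The eligibility checklist used under section 4.3 should be updated to match.

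The cost is a short amendment and a checklist revision. An occasional patient with a recently cured second cancer becomes ineligible, as the main clause already intends. Under reading (c) the deletion changes nothing.

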#### 3.3 Inclusion of Women and Minorities

Women and members of minority groups and their subpopulations will be included in this study.

## 4. REGISTRATION PROCEDURES

#### 4.1 Investigator and Research Associate Registration with CTEP

#### 4.1.1 CTEP Registration Procedures

Food and Drug Administration (FDA) regulations and National Cancer Institute (NCI) policy require all investigators participating in any NCI-sponsored clinical trial to register and to renew their registration annually.

Registration requires the submission of:

- a completed *Statement of Investigator Form* (FDA Form 1572) with an original signature
- a current Curriculum Vitae (CV)
- a completed and signed *Supplemental Investigator Data Form* (IDF)
- a completed *Financial Disclosure Form* (FDF) with an original signature

Fillable PDF forms and additional information can be found on the CTEP website at http://ctep.cancer.gov/investigatorResources/investigator\_registration.htm.

For questions about Investigator Registration, please contact the *CTEP Investigator Registration Help Desk* by email at [contact].

# 4.1.2 CTEP Associate Registration Procedures / CTEP-IAM Account

The Cancer Therapy Evaluation Program (CTEP) Identity and Access Management (IAM) application is a web-based application intended for use by both Investigators (*i.e.*, all physicians involved in the conduct of NCI-sponsored clinical trials) and Associates (*i.e.*, all staff involved in

the conduct of NCI-sponsored clinical trials).

Associates will use the CTEP-IAM application to register (both initial registration and annual reregistration) with CTEP and to obtain a user account.

Investigators will use the CTEP-IAM application to obtain a user account only. (See CTEP Investigator Registration Procedures above for information on registering with CTEP as an Investigator, which must be completed before a CTEP-IAM account can be requested.)

An active CTEP-IAM user account is required to access all CTEP applications and, if applicable (*e.g.*, all Network trials), all Cancer Trials Support Unit (CTSU) applications and websites.

Additional information can be found on the CTEP website at http://ctep.cancer.gov/branches/pmb/associate\_registration.htm.

For questions about Associate Registration or CTEP-IAM Account Creation, please contact the *CTEP Associate Registration Help Desk* by email at [contact].

## 4.2 Site Registration

This study is supported by the NCI Cancer Trials Support Unit (CTSU).

Each investigator or group of investigators at a clinical site must obtain Institutional Review Board (IRB) approval for this protocol and submit all required regulatory documents (including any protocol specific documents) to the CTSU Regulatory Office before they can be approved to enroll patients.

The CTSU Regulatory Office tracks receipt of these documents in the CTSU Regulatory Support System (RSS), reviews for compliance, and transmits site approval data to CTEP.

Sites participating on the NCI Central IRB (CIRB)-Early Phase initiative and accepting CIRB approval for the study are not required to submit separate IRB approval documentation to the CTSU Regulatory Office for initial, continuing, or amendment review. However, sites must submit a Study Specific Worksheet for Local Context (SSW) to the CIRB (via IRBManager) to indicate their intention to open the study locally. The CIRB's approval of the SSW is then communicated to the CTSU Regulatory Office for compliance in the RSS. The Signatory Institution must inform the CTSU which CIRB-approved institutions aligned with the Signatory Institutions. Other site registration requirements (*e.g.*, laboratory certifications, protocol-specific training certifications, or modality credentialing) must be submitted to the CTSU Regulatory Office or compliance communicated per protocol instructions.

#### 4.2.1 Requirements for 9925 Site Registration

• CTSU IRB Certification (for sites not participating via the NCI CIRB)

- CTSU IRB/Regulatory Approval Transmittal Sheet (for sites not participating via the NCI CIRB)
- Local informed consent document (if required by LPO)

# 4.2.2 Downloading Regulatory Documents

Site registration forms may be downloaded from the NCI #9925 protocol page located on the CTSU Web site. Permission to view and download this protocol is restricted and is based on person and site roster data housed in the CTSU RSS. To participate, Investigators and Associates must be associated with the Corresponding or Participating protocol organization in the RSS.

- Go to https://www.ctsu.org and log in using your CTEP IAM username and password.
- Click on the Protocols tab in the upper left of your screen.
- Click on the ETCTN link to expand, then select Phase 1 Grants, followed by LAO- NC010 and protocol #9925.
- Click on LPO Documents, select the Site Registration documents link, and download and complete the forms provided. (Note: For sites under the CIRB initiative, IRB data will automatically load to RSS.)

# 4.2.4 Checking Site Registration Status

Sites can check the status of their registration packets by querying the Site Registration subtab of the members' section of the CTSU Web site. (Note: Sites will not receive formal notification of regulatory approval from the CTSU Regulatory Office.)

- Go to https://www.ctsu.org and log in using your CTEP IAM username and password.
- Click on the Regulatory tab at the top of your screen.
- Click on the Site Registration subtab.
- Enter your 5-character CTEP Institution Code and click on Go.

Note: If possible, please allow three working days for site registration approval before attempting to enroll your first patient.

# 4.3 Patient Registration

In cooperation with the Corresponding Organization (Duke Cancer Institute LAO), the Lead Protocol Organization or LPO (Washington University School of Medicine) is utilizing an online 'study portal' for key study communication from participating sites to the Lead Principal Investigator and Study Coordinator. The study portal operates through REDCap, a secure, webbased application, managed by the Duke Cancer Institute LAO. Participating sites will not require REDCap user accounts or passwords to access the study portal for this study.

The 9925 Study Portal may be accessed through the following link: http://j.mp/2g4kpUG.

Prior to registering patients into Oncology Patient Enrollment Network (OPEN), participating sites are instructed to access the 9925 Study Portal for the following:

- **Subject Consent** Within 24 business hours of subject signing consent for the study, the Site Coordinator accesses the study portal to upload consents and notify the Study Coordinator of subject consent. Upon receipt of consent notification, the Study Coordinator will email the Site Coordinator with a subject screening ID number.
- Eligibility Confirmation After completion of all screening evaluations and if possible, within at least 48 business hours of anticipated study treatment start, the Site Coordinator accesses the study portal to upload completed eligibility checklist and de-identified supporting source documentation including sufficient tumor tissue pathology confirmation documentation. After review of eligibility documents by the Lead Principal Investigator or designee(s), the Study Coordinator will email the Site Coordinator with confirmation or questions/comments regarding subject eligibility. If eligibility is confirmed, the Site Coordinator will be instructed by the Study Coordinator via email to proceed to patient registration in OPEN.

# 4.3.1 OPEN / IWRS

Patient enrollment will be facilitated using the Oncology Patient Enrollment Network (OPEN). OPEN is a web-based registration system available to users on a 24/7 basis. It is integrated with the CTSU Enterprise System for regulatory and roster data interchange and with the Theradex Interactive Web Response System (IWRS) for retrieval of patient registration/randomization assignment. Patient enrollment data entered by Registrars in OPEN / IWRS will automatically transfer to the NCI's clinical data management system, Medidata Rave.

The OPEN system will provide the site with a printable confirmation of registration and treatment information. Please print this confirmation for your records.

# 4.3.2 **OPEN/IWRS** User Requirements

OPEN/IWRS users must meet the following requirements:

• Have a valid CTEP-IAM account (*i.e.*, CTEP username and password).

- To enroll patients: Be on an ETCTN Corresponding or Participating Organization roster with the role of Registrar.
- Have regulatory approval for the conduct of the study at their site.

Prior to accessing OPEN/IWRS, site staff should verify the following:

- All eligibility criteria have been met within the protocol stated timeframes.
- If applicable, all patients have signed an appropriate consent form and HIPAA authorization form.

